EudraVIGILANCE	European database for Pharmacovigilance
GCP	Good Clinical Practice

GMP	Good Manufacturing Practice
IB	Investigator Brochure
ICF	Informed Consent Form
ICH	International Conference on Harmonisation of technical requirements for registration of pharmaceuticals for human use.
IMP	Investigational Medicinal Product
IMPD	Investigational Medicinal Product Dossier
ISF	Investigator Site File (This forms part of the TMF)
ISRCTN	International Standard Randomised Controlled Trials Number
MA	Marketing Authorisation
MDT	Multidisciplinary Team
MHRA	Medicines and Healthcare products Regulatory Agency
MS	Member State
NHS R&D	National Health Service Research & Development
NIMP	Non-Investigational Medicinal Product
NICE	National Institute for Clinical Excellence
PI	Principal Investigator
PIC	Participant Identification Centre
PIS	Participant Information Sheet
QA	Quality Assurance
QC	Quality Control
QP	Qualified Person
RCT	Randomised Control Trial
REC	Research Ethics Committee
SAE	Serious Adverse Event
SAR	Serious Adverse Reaction
SDV	Source Data Verification
SOP	Standard Operating Procedure
SmPC	Summary of Product Characteristics
SSI	Site Specific Information
SUSAR	Suspected Unexpected Serious Adverse Reaction
TMF	Trial Master File
TMG	Trial Management Group
TSC	Trial Steering Committee

ii. TRIAL SUMMARY

Trial Title	An Open Label Randomised Trial to Assess the Efficacy of Post-Operative Ferric Maltol Vs Standard Care for Anaemia Following Colorectal Cancer Surgery	
Short title	PICoC Trial – Perioperative Iron in Colorectal Cancer	
Clinical Phase	Feasibility	
Trial Design	Open label randomised controlled trial	
Trial Participants	Anaemic patients with colorectal adenocarcinoma undergoing surgery	
Planned Sample Size	40 participants	
Treatment duration	12 weeks from completion of surgery	
Follow up duration	12 weeks	
Planned Trial Period	24 months	
	Objectives	Outcome Measures
Primary	Feasibility measures	
 • Eligible patients from screening • Study exclusion • Acceptability of recruitment • Study retention
Secondary	
 1. To compare change in blood indices between intervention and control groups. 2. To compare quality of life between groups. 3. To compare post-operative complications, survival and length of stay between intervention and control groups. 4. To compare allogenic red blood cell transfusion use between groups. 5. Tolerability of ferric maltol. 	
 1. Change in haemoglobin and haematinic markers 2. Quality of life as determined by the SF36, EQ-5D and FACT-An questionnaires 3. Post-operative morbidity and mortality and length of stay 4. Post-operative allogenic blood transfusion. 5. Side-effects and reactions to ferric maltol
IMP	Ferric Maltol (Feracceu)	
Dose, Route of Administration	Oral tablets, 30mg dose twice daily.	

iii. FUNDING AND SUPPORT IN KIND

FUNDER(S)	FINANCIAL AND NON FINANCIAL SUPPORT GIVEN
(Names and contact details of ALL organisations providing funding and/or support in kind for this trial)	
Norgine Ltd	An unrestricted open commercial grant to fully support trial delivery and consumables

iv. ROLE OF TRIAL SPONSOR AND FUNDER

The Royal Wolverhampton NHS Trust is the sponsor of this study and assumes overall responsibility for the initiation, and management of the study.

Funding and drug supply for the study (Ferric iron) has been provided by Norgine Pharmaceuticals Ltd.

Protocol contributors

[figure not shown]
The study design, conduct, data analysis and interpretation, manuscript writing, and result dissemination will be the responsibility of the research team, overseen by the sponsor.

The protocol will be reviewed by Norgine Ltd. prior to ethics submission but they will not be involved in the study conduct, data analysis or interpretation

Anaemia, Colorectal Cancer, Ferric maltol, Iron, Peri-operative

v. KEY WORDS:

vi. TRIAL FLOW CHART

1 BACKGROUND

Colorectal cancer is associated with iron deficiency anaemia in 40-60% of cases (Leichtle, Mouawad et al. 2011). This anaemia can lead to poorer post-operative outcomes such as higher complication rates, increased length of stay and reduced survival (Muñoz, [name] et al. 2018). There has been a recent shift towards the correction of preoperative anaemia in order to optimize perioperative outcomes. However, despite improvements in preoperative haemoglobin there exists a group of patients who develop worsening or recurrent anaemia in the post-operative period. Without intervention up to 90% of patients in the immediate postoperative period may develop anaemia (Shander, Knight et al. 2004). This is not unexpected given the peri-operative blood loss; poor nutritional intake in the postoperative period; and the frequent blood sampling for laboratory tests. Our data from previous trials has demonstrated that despite preoperative intravenous iron therapy 75% of patients remain anaemic at the time of their colorectal cancer operation (Keeler, Simpson et al. 2017). In addition, our unpublished data has found that around 1/3 of patients treated with preoperative iron therapy develop a recurrence of their anaemia in the first year postoperatively. Studies have identified that traditional oral ferrous iron supplementation is largely ineffective (Bisbe et al. 2014) for the treatment of postoperative anaemia. However, a newer oral iron preparation - ferric maltol (Ferracru) has been found to be better tolerated and more efficacious than ferrous iron (Schmidt, Ahmad et al. 2016, Oppong, Lovato et al. 2018). This study aims to evaluate whether the use of iron supplementation in the form of Feracru could lead to a more sustained or improved a response in haemoglobin if given after a colorectal cancer operation. Improving this postoperative anaemia may have important implications for clinician and patient reported outcomes. The Perioperative Iron in Colorectal Cancer (PICoC) trial will run as a feasibility study to assess the proposed design, recruitability and outcome measures. Anaemic colorectal cancer patients treated with

preoperative intravenous iron will be randomised in an open label design to receive a course of Ferric maltol (intervention group) or standard care (control group) postoperatively. Secondary outcome measures will focus on a comparison of change in blood indices, quality of life, allogenic red blood transfusion rates and postoperative complications between groups. Follow up will continue until the first postoperative outpatient visit at approximately 12 weeks following discharge.

2 RATIONALE

The PICoC study aims to investigate whether oral ferric maltol given postoperatively offers an improvement in patient and clinician reported outcomes compared to standard care. If postoperative anaemia can be improved this could lead to fewer complication rates, better quality of life and a shorter length of stay in colorectal cancer patients after operation.

Traditionally oral ferrous (Fe^{2+}) iron preparations, such as ferrous fumarate or ferrous sulphate have been used to treat iron deficiency anaemia. However, these forms of iron supplementation can damage the gut mucosa by the process of oxidative stress leading to symptoms of abdominal pain, nausea, constipation or diarrhoea.

Ferric maltol is a novel oral iron therapy which has shown promise as an effective treatment for iron deficiency anaemia in conditions such as inflammatory bowel disease (Gasche, Ahmad et al. 2014). After oral ingestion of ferric maltol, ferric iron reaches the intestinal mucosa as a complex, allowing more efficient absorption of ferric iron by the gut compared to ferrous iron (Levey, Barrand et al. 1988), even at a low dose. This is also thought to lead to a more favourable side effect profile with patients (Schmidt, Ahmad et al. 2016, Oppong, Lovato et al. 2018)

Current standard care involves monitoring for signs of worsening anaemia in the postoperative period with the option of transfusing allogenic blood (ARBT) if the clinical need

arises. Existing NICE guidance advises a haemoglobin threshold of 70g/L to trigger ARBT. This leaves a large number of postoperative anaemic patients without an effective treatment leading to higher complication rates, increased length of stay. In addition, where transfusions are used they carry a small but significant risk of infection, immune reaction as well as a high cost. Studies have also drawn links between ARBT and cancer recurrence (Amato and Pescatori 2006, [name], [name] et al. 2012).

Owing to the change in stool colour with oral iron supplementation it is not possible to blind patients to the study group allocation and therefore the intervention will be compared to standard care rather than placebo.

3 OBJECTIVES AND OUTCOME MEASURES/ENDPOINTS

3.1 Primary objective

To determine the feasibility of a phase IV open label, controlled multi-centre randomised trial of oral ferric maltol versus standard care postoperatively for colorectal cancer patients who have been treated with preoperative intravenous iron for anaemia. Feasibility measures will include:

- Eligible patients from screening
- Study exclusion
- Acceptability of recruitment
- Study retention

3.2 Secondary objectives

- To investigate whether the use of ferric maltol could improve the postoperative quality of life of patients after colorectal cancer surgery compared to standard care.

- To calculate the change in postoperative haemoglobin and haematinics in response to ferric maltol compared to standard care.
- To compare postoperative allogenic red blood cell transfusion rates in patients receiving ferric maltol or standard care
- To review the tolerability of ferric maltol for the treatment of postoperative colorectal cancer patients
- To compare length of stay and complication rates in patients receiving ferric maltol or standard care postoperatively.
- To assess for immunological and metabolomic peri-operative differences between patients receiving ferric maltol preparations and standard care.

3.3 Outcome measures/endpoints

3.3.1 Primary endpoint/outcome

Study feasibility will be the primary endpoint. No a priori criteria will be used to determine study feasibility. We will use the data generated by PICoC to determine the sample size and outcome measures of a definitive trial

3.3.2 Secondary endpoints/outcomes

1. Levels of haemoglobin and haematinic markers (full blood count, ferritin, iron, transferrin, and transferrin saturation). Immunological and metabolomic markers will also be assessed. These will be measured at a point preoperatively before intravenous iron treatment, on the day of surgery and at defined time points postoperatively during the administration of oral ferric maltol or during standard care
2. Side-effects and reactions to ferric maltol administration
3. Peri- and post-operative morbidity and mortality
4. Post-operative complications

5. Post-operative length of stay
6. Post-operative allogenic blood transfusion.
7. Quality of life as determined by the SF36, EQ-5D and FACT-An questionnaires.

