9 PHARMACOVIGILANCE

9.1 Definitions

9.1.1 Adverse Event (AE)

An AE or adverse experience is:

Any untoward medical occurrence in a patient or clinical investigation in participants administered a medicinal product, which does not necessarily have to have a causal relationship with this treatment (the study medication).

An AE can therefore be any unfavourable and unintended sign (including an abnormal laboratory finding), symptom or disease temporally associated with the use of the study medication, whether or not considered related to the study medication.

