9.1.5 Expected Serious Adverse Events/Reactions

Serious adverse events that could be expected during the course of the study according to the SmPC include vomiting, haematemesis, gastrointestinal perforation, abdominal pain and dysphagia which could be related to the progression of the disease. Adverse events may also be anticipated in relation to any postoperative chemotherapy used. These would include anaemia, neutropenia (and consequences of sepsis), thrombocytopenia (and consequences of

coagulopathy), rashes, photosensitivity, taste/hearing disturbance, hair loss, discoloured urine, diarrhoea, oral ulceration and renal failure. These adverse events will be recorded in the CRF as significant clinical events.

Events which are not deemed secondary to the underlying cancer will be reported to the sponsor as a Serious Adverse Event within 24 hours of the Investigator becoming aware of the event.

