9.1.6 Suspected Unexpected Serious Adverse Reactions

A serious adverse reaction, the nature or severity of which is not consistent with the applicable product information as stated in the reference safety information in the SmPC that follows:

Common symptoms: “Abdominal pain (including upper abdomen), Flatulence, Constipation, Abdominal discomfort/ distension, Diarrhoea, Discoloured faeces, Nausea”

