9.2 Recording and reporting of SAEs, SARs AND SUSARs

All AEs occurring during the study observed by the investigator or reported by the participant, whether or not attributed to study medication, will be recorded on the CRF. These adverse events will be recorded in the CRF. All SAEs assigned by the PI or delegate (or following central review) as both suspected to be related to IMP-treatment and unexpected will be classified as SUSARs and will be subject to expedited reporting to the Medicines and Healthcare Products Regulatory Agency (MHRA). The sponsor will inform the MHRA, the REC and Marketing Authorisation Holder (if not the sponsor) of SUSARs within the required expedited reporting timescales. All related AEs that result in a participant’s withdrawal from the study or are present at the end of the study, will be followed up until a satisfactory resolution occurs.

It will be left to the investigator’s clinical judgment whether or not an AE is of sufficient severity

to require the participant's removal from treatment. A participant may also voluntarily withdraw from treatment due to what he or she perceives as an intolerable AE. If either of these occurs, the participant will undergo an end of study assessment and be given appropriate care under medical supervision until symptoms cease or the condition becomes stable.

The severity of events will be assessed according to the Common Terminology Criteria for Adverse Events (CTCEA V 5.0) the following scale:

- Grade 1 Mild; asymptomatic or mild symptoms; clinical or diagnostic observations only; intervention not indicated.
- Grade 2 Moderate; minimal, local or non-invasive intervention indicated; limiting age appropriate instrumental ADL.
- Grade 3 Severe or medically significant but not immediately life-threatening; hospitalization or prolongation of hospitalization indicated; disabling; limiting self-care ADL.
- Grade 4 Life-threatening consequences; urgent intervention indicated.
- Grade 5 Death related to AE

The relationship of AEs to the study medication will be assessed by a medically qualified investigator. Any pregnancy occurring during the clinical study and the outcome of the pregnancy, will be recorded and followed up for congenital abnormality or birth defect.

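### Tolerability is worded as reactions to ferric maltol, so it has no control-arm value and rests on unblinded attribution, and no between-arm analysis is named

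*Combined protocol and SAP*

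**What the plan says.** The endpoint in section 3.3.2 is "Side-effects and reactions to ferric maltol administration", and the Trial Summary uses nearly the same words. The matching objective in section 3.2 is "To review the tolerability of ferric maltol for the treatment of postoperative colorectal cancer patients". It names no comparator, whereas the objectives beside it on quality of life, blood indices, transfusion, and length of stay with complications all name standard care.

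Section 10.3.3 covers transfusion, blood indices and quality of life; neither tolerability nor adverse events appear. Section 10.2 says in general terms that change in the secondary outcome measures will be shown between the groups.

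Section 9.1.6 gives the known common reactions: "Abdominal pain (including upper abdomen), Flatulence, Constipation, Abdominal discomfort/ distension, Diarrhoea, Discoloured faeces, Nausea". Section 9.1.5, on expected serious events, lists "vomiting, haematemesis, gastrointestinal perforation, abdominal pain and dysphagia which could be related to the progression of the disease", and adds: "Adverse events may also be anticipated in relation to any postoperative chemotherapy used". Diarrhoea is among the chemotherapy events it then names.

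On data capture, section 9.2 says that the CRF will record "All AEs occurring during the study observed by the investigator or reported by the participant, whether or not attributed to study medication", and that a medically qualified investigator will judge the relationship to study medication. Section 7.4 says that patient and investigator are unblinded. Appendix 1 schedules adverse event assessments at Visits 2 to 7 without restricting them to one arm. Section 9.1.1 describes an adverse event as "temporally associated with the use of the study medication, whether or not considered related to the study medication". Under section 8.5, treatment starts once anaemia is confirmed on day 2, 3 or 5 after surgery and oral intake has resumed.

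**The concern.** A control patient cannot react to a drug that was not taken. As worded, the endpoint is a count in one arm, and each event enters it only if someone who knows the allocation ascribes it to the drug. At least some of the listed symptoms can arise for other reasons in the same weeks. The count could therefore make the drug look poorly tolerated when controls have the same symptoms, or hide real intolerance that was put down to recovery.

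This matters beyond one table. The Background cites better tolerability than ferrous iron as a reason to study ferric maltol, and the Rationale names abdominal pain, nausea, constipation and diarrhoea as the problems with ferrous iron. Section 3.3.1 says that the data will shape the outcome measures of a definitive trial, so a one-arm definition could be carried forward.

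**Working it through.** The plan has no figure for tolerability to reproduce. Section 10.1 states that no sample size calculation was done; the only arithmetic is 20 per arm × 2 = 40.

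**Step 1. Overlap between the two lists.** Section 9.1.6 has seven terms.

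| 9.1.6 term | Also in 9.1.5? |
|---|---|
| Abdominal pain | Yes, with disease progression |
| Diarrhoea | Yes, with chemotherapy |
| Flatulence | No |
| Constipation | No |
| Abdominal discomfort/distension | No |
| Discoloured faeces | No |
| Nausea | No |

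The overlap is 2 of 7. That flatulence, constipation, distension or nausea also follow bowel surgery is plausible, but section 9.1.5 does not say so; it is an assumption here.

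**Step 2. Does the general statement in 10.2 supply the comparison?** It speaks of change in outcome measures between groups. Reactions to ferric maltol have no baseline value to change from and no value in controls. Applied literally, it would set the treated count against a zero that is fixed by definition.

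**Step 3. What a treated-arm figure can show.** Inputs: n = 20 per arm (section 10.1). The event counts are assumptions, because the documents give none. Wilson 95% interval with z = 1.96, so z² = 3.84:

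- centre = (p + z²/2n) / (1 + z²/n)
- half-width = z·√(p(1−p)/n + z²/4n²) / (1 + z²/n)

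For 8/20, p = 0.40:

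- centre = (0.400 + 0.096)/1.192 = 0.416
- half-width = 1.96·√(0.0120 + 0.0024)/1.192 = 0.197
- interval = 0.22 to 0.61

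The same 40% is compatible with different drug effects:

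- controls 8/20: 40 − 40 = 0 points
- controls 4/20: 40 − 20 = 20 points

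Nothing in the treated arm tells these two cases apart.

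**Step 4. What the two-arm comparison would show.** The Newcombe interval combines the Wilson limits (l, u) of each arm, where p₁ is treated, p₂ is control and d = p₁ − p₂:

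- lower = d − √((p₁ − l₁)² + (u₂ − p₂)²)
- upper = d + √((u₁ − p₁)² + (p₂ − l₂)²)

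For 8/20 against 6/20, the Wilson limits are 0.219 to 0.613 and 0.146 to 0.519:

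- lower = 0.10 − √(0.181² + 0.219²) = 0.10 − 0.284 = −0.18
- upper = 0.10 + √(0.213² + 0.154²) = 0.10 + 0.263 = +0.36

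| Treated | Control | Difference (points) | 95% CI |
|---|---|---|---|
| 8/20 | 8/20 | 0 | −28 to +28 |
| 8/20 | 6/20 | 10 | −18 to +36 |
| 8/20 | 4/20 | 20 | −8 to +44 |

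The comparison removes the shared background in expectation, but at this size it can only be descriptive.

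**The case against.** The strongest reply is that the trial already has what it needs. It randomises 1:1 against concurrent standard care (section 7.3), records all adverse events whatever their attribution (section 9.2), and assesses them at Visits 2 to 7 in all participants (Appendix 1). Complications and morbidity are separate endpoints, and complications are compared between arms. Tolerability is also informed by reasons for non-compliance (8.8), reasons for withdrawal (7.8), and withdrawal and compliance as feasibility measures (10.3.2). For one secondary outcome of a descriptive feasibility trial, this is a gap in wording.

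Much of that stands, and it rules out four stronger readings that a reader might reach:

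- **That the design makes drug effect inseparable from the postoperative course.** It does not. Both arms' symptoms are scheduled for collection; the gap is in the endpoint definition and the analysis plan.
- **That section 9.1.5 links the listed reactions as a group to disease or chemotherapy.** It covers two of seven, and it concerns serious events, whereas 9.1.6 lists common symptoms.
- **That control-arm symptoms do not count as adverse events under 9.1.1.** That reading is strained. Appendix 1 assesses adverse events at baseline and on the day of surgery, before anyone takes the drug, so capture cannot depend on use. The wording is only unclear.
- **That the tolerability objective goes unanswered.** The objective is to review tolerability, and the other planned information bears on it.

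What the reply does not remove is that no section says the symptom data will be tabulated by arm, and the endpoint as named is an attributed count in one arm.

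**Conclusion.** The point holds as a cheap improvement to the definition and analysis of one secondary endpoint. As written, the plan yields an uncontrolled count that depends on unblinded attribution, although the control data needed to interpret it are due to be collected.

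The size cannot be stated from the documents, which give no symptom rates. On the assumed 8/20, the treated-arm figure fits an excess of 0 or of 20 points equally well. The conclusion needs only that some of the listed symptoms occur without the drug. The protocol allows this for two of the seven terms, and for the other bowel symptoms it is a plausible assumption. A by-arm display gives a better estimate of drug effect, but not a precise one.

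**What to change.** - **Sections 3.3.2 and 10.3.3.** Define tolerability as the occurrence and CTCAE grade of the 9.1.6 symptoms from any cause, in both arms, from entry into the allocated pathway to the final visit. Show each symptom by arm with the difference and its 95% CI, labelled descriptive. Pathway entry depends on the postoperative haemoglobin result in both arms, so it is a common starting point. Randomisation is not: section 4 places it before the operation and section 7.7 after it.
- **Discoloured faeces.** Show it separately, since section 7.4 treats stool colour as what reveals the allocation.
- **Attributed reactions and discontinuations of the drug.** Keep these as treated-arm listings.
- **Section 9.1.1.** State that adverse events are collected in both arms throughout the study, and keep the assessments made before treatment.
- **CRF.** Put the same symptom list to both arms at the assessments already in Appendix 1.

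The cost is protocol and CRF wording plus a few minutes per visit, with no new visits. Three limits remain and should be stated in the plan: symptom reporting is subjective in an open-label trial; no adverse event visit falls between day 5 and weeks 8 to 12, so recall is long in both arms; and precision at 20 per arm is low.
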